### 8.1. Subject Inclusion Criteria

1. Male and female subjects age  $\geq$  18 years.
2. The subject must meet one of the following two criteria:
  - a. A positive influenza Rapid Antigen Test (RAT) and/or a FDA-approved PCR test and at least one clinical sign or symptom consistent with acute influenza infection as listed in 2b below.

**OR**

- b. Clinical signs and symptoms consistent with acute influenza infection consisting of an oral temperature  $\geq$  100°F (37.8°C) with at least one respiratory symptom of at least moderate severity (cough or rhinitis) and at least one constitutional symptom of at least moderate severity (myalgia [aches and pains], headache, feverishness, or fatigue). **Note: Enrollment at each site by clinical symptoms alone will be approved by the Sponsor at the beginning of each influenza season once influenza has been confirmed in the local community. The Sponsor may withdraw approval for symptomatic screening in any season based upon trends in influenza surveillance data. Prior to Sponsor approval or after approval is withdrawn, Criteria 2 must be met by a positive influenza RAT test and/or PCR. During the period of approval, clinical symptoms alone will be adequate to meet Criteria 2.**
3. Onset of symptoms no more than 48 hours before presentation for screening. However, due to historically delayed presentation for medical care in the adult population, approximately 20% of the elderly population may be enrolled with symptoms starting  $>$  48-hours but  $\leq$  72-hours prior to presentation for screening. Note: Time of onset of illness is defined as either (1) the time when the temperature (either oral or rectal) was first measured as elevated (at least one °C of elevated temperature), OR (2) the time when the subject experienced the presence of at least one respiratory symptom AND the presence of at least one constitutional symptom together.
4. Either age  $\geq$  65 years AND/ OR presence of one of the following risk factors:
  - a. Pregnancy, including women who are up to 2 weeks postpartum
  - b. Resident of a nursing home or long-term care facility
  - c. History of chronic lung disease including obstructive pulmonary disease (COPD), persistent asthma or cystic fibrosis
  - d. History of heart disease including myocardial infarction, angina requiring treatment, congestive heart failure requiring treatment, arrhythmia including atrial fibrillation and valvular dysfunction

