1.1. STUDY OVERVIEW

Protocol BCX1812-306 is a multicenter, single-arm, open-label study to evaluate the safety, PK, and effectiveness of a single dose of peramivir administered intravenously (IV) in elderly subjects (≥ 65 years of age) with acute uncomplicated influenza and in younger subjects (< 65 years of age) with acute uncomplicated influenza who are at higher risk for influenza complications. Elderly subjects will not be classified as high or low risk and will be captured as elderly only.

Approximately 120 subjects will be enrolled in this open-label study (a minimum of 80 elderly subjects will be enrolled). A subject's duration of participation in this study is expected to be 14 days and will include up to 4 clinic visits. It is expected that most subjects will have the Screening visit and the Day 1 Treatment visit on the same day. Following treatment on study Day 1, subjects will undergo follow-up assessments on Days 3, 7, and 14 in the clinic. Subjects will be discharged from this study on Day 14. Additional unscheduled visits may be required for subjects who report symptoms of influenza of moderate or severe intensity at Day 14 or have persistent adverse events (AEs) and/or treatment-emergent laboratory findings that require medical monitoring or management.

Eligible subjects will have a positive influenza Rapid Antigen Test (RAT) and/or a Food and Drug Administration (FDA) approved polymerase chain reaction (PCR) test and at least one clinical sign or symptom consistent with influenza OR clinical signs and symptoms consistent with acute influenza infection consisting of an oral temperature $\geq 37.8^{\circ}\text{C}$ / 100°F with at least one respiratory symptom of at least moderate severity (cough or rhinitis) and at least one constitutional symptom of at least moderate severity (myalgia, headache, feverishness, or fatigue).

Subjects will receive a single IV dose of 600 mg peramivir (or less if renally impaired), which will occur over 15 to 30 minutes.

An adequate nasal swab specimen will be collected from all enrolled subjects at Baseline (predose) for virus subtype identification and quantitative virologic assessments and at the follow-up assessments on study Days 3, 7, and 14.

Specimens obtained from all subjects on Day 1 and the last specimen that yields influenza virus on culture will also be assessed for susceptibility to neuraminidase inhibitors. A central laboratory will perform all virologic assessments.

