3.3.8. Definitions and Terminology

Age

Age will be defined as the age in years at time of signing of informed consent for all subjects.

Confirmed Influenza

A subject will be confirmed as having acute influenza infection if any specimen for assay of influenza A or B antigen by RT-PCR obtained during the study is positive.

Baseline Value

For purposes of analysis, the baseline value is defined as the last value obtained prior to initiation of study drug (eg, the Baseline Pre-Dose value). Should this value be obtained after the injection of study drug, then the most recent value obtained prior to initiation of study drug will be used for the baseline value.

Day 1

Day 1 is the day/time that study drug is initiated.

Study Day

Study Day is defined relative to Baseline (Day 1). Thus, the study day of an event is calculated as:
Study Day = event date – date of Day 1 +1.

Days on Study

Days on Study is the number of days from Day 1 to the date of study completion or early termination as recorded on the Day 14/End of Study/Early Withdrawal CRF.

Days of Subject Diary Completion

Days of Subject Diary Completion is defined as the number of days from Day 1 to the date of last Subject Diary completion. For the purposes of this analysis, the date of last Subject Diary completion is defined as the last date in which the Subject Diary had at least one complete assessment of symptoms recorded.

Alleviation of Symptoms

A subject has Alleviation of Symptoms if all of the assessed symptoms of influenza assessed on his/her subject diary are either absent or are present at no more than mild severity level and at this status for a 21.5 hour period (24 hours less 10%).

Composite Symptom Score

The Composite Symptom Score is defined as the sum of the seven symptoms of influenza (cough, sore throat, stuffy nose, muscle aches, headache, feverishness, fatigue/tired) assessed on a given time point within the subject diary.

Baseline Composite Symptom Score

The Baseline Composite Symptom Score is defined as the sum of the symptoms of influenza recorded by the subject in the diary corresponding to the assessment of a subject's symptoms prior to the initiation of study drug.

Resolution of Fever

A subject has Resolution of Fever if he/she has a temperature < 37.4°C/99.4°F oral and no antipyretic medications have been taken for at least 12 hours. Resolution of Fever is based on information obtained from the individual subject diaries.

Ability to Perform Usual Activities

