The ability to perform usual activities is defined as a subject rating of 10 (able to perform all usual activities fully) on the visual analog scale the subject uses to rate his or her current ability to perform usual activities compared with normal ability.

Time to Event

Time to a given event is defined as the number of hours (days) from initiation of earliest study treatment until the event occurs. The unit of measurement will vary based upon the endpoint and its respective schedule of assessment.

Time to Alleviation of Symptoms

Time to Alleviation of Symptoms is the number of hours from initiation of study drug to start of the 21.5 hour period (24 hours less 10%) where all symptoms of influenza are recorded as none or mild.

Change from Baseline

Change from baseline for a given endpoint is defined as the Study Day X value minus the Baseline Value.

Adverse Event (AE)

According to the protocol, an AE is any untoward medical occurrence in a clinical study subject. No causal relationship with the study drug or with the clinical study itself is implied. An AE may be an unfavorable and unintended sign, symptom, syndrome, or illness that develops or worsens during the clinical study. Clinically relevant abnormal results of diagnostic procedures including abnormal laboratory findings (eg, requiring unscheduled diagnostic procedures or treatment measures, or resulting in withdrawal from the study) are considered to be AEs.

AEs may be designated as “nonserious” or “serious” (see Protocol Section 11.1.1.1). Surgical procedures are not AEs but may constitute therapeutic measures for conditions that require surgery. The condition for which the surgery is required is an AE if it occurs or is detected during the study period. Planned surgical measures permitted by the clinical study protocol and the condition(s) leading to these measures are not AEs if the condition(s) was (were) known before the start of study treatment. In the latter case the condition should be reported as medical history.

Assessment of symptoms of influenza will be documented in a Subject Diary and analyzed as a measure of effectiveness of the study treatment. These symptoms will not be reported as AEs unless the symptom(s) worsen to the extent that the outcome fulfills the definition of a serious adverse event (SAE), which then must be recorded as such (see Protocol Section 11.1.1.2).

All AEs will be recorded on the ADVERSE EVENTS CRF.

Treatment-emergent Adverse Events (TEAEs)

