4.2. INTENT-TO-TREAT INFECTED POPULATION

The ITTI population will include all subjects who are enrolled, treated, and have influenza type A or B confirmed by PCR. The ITTI population will be used for analyses of effectiveness.

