5.2.2. Effectiveness Analyses

A subject's oral temperature taken by subjects and recorded in the diary by subjects/caregivers will be summarized by age group and overall by study visit. A subject has Resolution of Fever if he/she has an oral temperature $< 37.4^{\circ}\text{C}/99.4^{\circ}\text{F}$ oral and no antipyretic medications have been taken for at least 12 hours. The time to resolution of fever will be estimated for each age group and overall using the Kaplan-Meier method with temperature and symptom relief medication information obtained from the subject diary data. Subjects who do not have resolution of fever will be censored at the time of their last non-missing post-baseline temperature assessment.

Alleviation of symptoms will be determined by assessment of symptoms as reported on each Subject Diary. The time to alleviation of symptoms, defined as the time from initiation of study drug until the start of the 21.5 hour period (24 hours less 10%) where all symptoms of influenza are recorded as none or mild, will be estimated overall and for each age group using the Kaplan-Meier method. Subjects who do not experience alleviation of symptoms will be censored at the date of their last non-missing post-baseline assessment.

Change from baseline in \log_{10} TCID₅₀/mL through Day 3, Day 7, and Day 14 will be presented by age group and overall for subjects with positive viral titers at baseline (\log_{10} TCID₅₀/mL > 0.5). A box plot and a histogram of the TCID₅₀/mL values will be presented by visit and age group. In addition, the median change from baseline in TCID₅₀/mL will be presented by visit and age group.

The number and percent of subjects with positive viral titers at baseline (\log_{10} TCID₅₀/mL > 0.5) that shed virus at each visit will be presented by age group and overall.

The RT-PCR results at each visit will be presented by age group and overall for subjects with positive RT-PCR results at baseline.

Change from baseline to last positive value of influenza virus susceptibility to neuraminidase inhibitors will be assessed using virology laboratory tests. Virology laboratory tests will include phenotypic characterizations of influenza virus recovered (hemagglutinin and neuraminidase) and viral susceptibility to zanamivir, oseltamivir, and peramivir, as well as genotyping of virus isolates. These analyses will be presented overall and by age group and viral subtype.

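### Time to alleviation of symptoms has no baseline severity condition, so it can count subjects who were already at none or mild before dosing

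*SAP*

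**What the plan says.** **Event.** SAP 3.3.8 counts a subject as alleviated when all assessed diary symptoms "are either absent or are present at no more than mild severity level and at this status for a 21.5 hour period". The clock runs from dosing to the start of that period: "Time to Alleviation of Symptoms is the number of hours from initiation of study drug to start of the 21.5 hour period".

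**Estimator.** Under SAP 5.2.2 the time "will be estimated overall and for each age group using the Kaplan-Meier method".

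**Analysis set.** SAP 4.2: "The ITTI population will include all subjects who are enrolled, treated, and have influenza type A or B confirmed by PCR". It adds: "The ITTI population will be used for analyses of effectiveness". Neither sentence sets a symptom condition.

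**Entry.** Criterion 2a in Protocol 8.1 asks for a positive rapid antigen or PCR test and "at least one clinical sign or symptom consistent with acute influenza infection as listed in 2b below". SAP 1.1 restates this as a positive test "and at least one clinical sign or symptom consistent with influenza", with no severity. Criterion 2b asks for an oral temperature of at least 100°F plus one respiratory and one constitutional symptom, each at least moderate. Protocol 10.1.1 sets out both routes. It then adds that a subject needs one respiratory and one constitutional symptom of at least moderate severity to be eligible, without limiting this to one route.

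**The concern.** A time-to-alleviation endpoint is informative only for a subject who has something to alleviate. As defined, a subject can be in the event state at the moment of dosing, and the SAP has no rule to exclude, censor or separate such subjects. If the state holds through the first 21.5 h, the event time is about that of the first post-dose diary entry, whatever the drug does.

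SAP 5.2.2 applies the missing principle to its virology endpoints. Titre change and shedding are summarised only for subjects with a positive titre at baseline, and RT-PCR results only for subjects RT-PCR positive at baseline. The symptom endpoint has no matching condition.

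The study has one arm, so no control group carries the same artefact. The medians, overall and by age group, are the reported result. The same times also form one axis of the exposure-response scatter plot (Figure 14.4.2).

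**Working it through.** **Step 1: can such a subject enter?**

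- *Route 2b.* No, on any reading. Two symptoms must be at least moderate at Screening.
- *Route 2a, Protocol 8.1.* One listed sign or symptom is enough. The reference to 2b may carry the moderate threshold over to symptoms. However, 2b also lists measured oral temperature, which is a sign and is not one of the seven diary symptoms in Protocol 10.2.2 (feverishness, a rating, is). A positive test with measured fever and otherwise mild symptoms can therefore qualify.
- *Route 2a, SAP 1.1.* No severity is stated, so a mild symptom can qualify.
- *Protocol 10.1.1.* If its last eligibility sentence applies to everyone, no subject is all absent or mild on the Screening rating.

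The last line conflicts with the two before it. Route 2a is also the only route at a site before the Sponsor approves enrolment on symptoms alone, or after it withdraws approval (Protocol 8.1), so it need not be rare.

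**Step 2: effect on the median.** The plan states no figure to reproduce: there is no hypothesis test, and the 120 subjects come from no formal calculation.

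Inputs, all assumed because the documents give none:
- *f*, the share of ITTI subjects already at none or mild who stay there for 21.5 h: 0% to 20%.
- *M*, the median in the other subjects: 60 to 100 h for illustration. Results are also shown as a ratio to *M*.
- Shape of the other subjects' times: exponential, Weibull (shape 1.5) or lognormal (log-SD σ of 0.6, 0.8 or 1.0).

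The share *f* has its event near time 0 and the rest have survival S(t). The observed median t solves (1 − f) × S(t) = 0.5. It does not matter exactly when the first diary entry falls, provided it comes before the median.

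- Exponential: t/M = 1 + log₂(1 − f). At f = 10%: 1 + log₂(0.9) = 0.848.
- Weibull 1.5: t/M = [1 + log₂(1 − f)]^(1/1.5). At f = 10%: 0.848^(1/1.5) = 0.896.
- Lognormal: t/M = exp(σ × z), where z is the standard normal quantile of (0.5 − f)/(1 − f). At f = 10% the probability is 0.4/0.9 = 0.444 and z = −0.140; with σ = 0.6 the ratio is exp(−0.084) = 0.920.

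| f | Exponential | Weibull 1.5 | Lognormal σ 0.6 / 0.8 / 1.0 | Fall in median |
|---|---|---|---|---|
| 0% | 1.000 | 1.000 | 1.000 / 1.000 / 1.000 | 0% |
| 5% | 0.926 | 0.950 | 0.961 / 0.949 / 0.936 | 4-7% |
| 10% | 0.848 | 0.896 | 0.920 / 0.894 / 0.870 | 8-15% |
| 20% | 0.678 | 0.772 | 0.826 / 0.775 / 0.727 | 17-32% |

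In hours, the exponential case (the largest fall in each row) at f = 10% is about 9 h if M = 60 h (60 × 0.152) and 15 h if M = 100 h (100 × 0.152).

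**The case against.** The strongest reply is Protocol 10.1.1. Its sentence follows both routes, names only symptoms that the diary also rates, and says they must be at least moderate for eligibility. Applied to all, it puts the share at zero on the Screening rating. This stands as a reason not to treat the bias as established. It does not settle the matter:

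- Protocol section 8 ties eligibility to the listed criteria. Neither 8.1, the synopsis nor SAP 1.1 contains the sentence.
- Applied to all, it would empty the single sign or symptom in 2a of meaning.
- Screening ratings are made by study personnel, while the endpoint uses the subject's diary. The two can differ.

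Second, an all-mild subject may worsen. Most enter within 48 h of onset, and one who worsens in the first 21.5 h gets a later and informative event time. This also stands: the percentages assume that none does, so they are upper figures for a given baseline share.

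Third, the endpoint is one of several secondary endpoints, summarised descriptively in a study whose primary endpoint is safety, and the exposure-response plot is exploratory. That limits the weight of the point, but the defect remains.

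A reader might go further and infer that the endpoint does include such subjects, or that the displays by age are distorted because entry routes differ by age. The documents support neither: they give no count of subjects at none or mild and no split of entry route by age.

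**Conclusion.** The gap in the SAP is real. Time to alleviation has no baseline severity condition and no rule for subjects already in the event state, and the eligibility passages conflict on whether such subjects can enrol. The direction is clear: any who enter and stay at none or mild lower the median.

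The size is unknown. It runs from no effect, if 10.1.1 binds every subject and diary and staff ratings agree, to falls of 4-7%, 8-15% and 17-32% at assumed shares of 5%, 10% and 20%. These figures rest on the assumed shares, the assumed distributions and no worsening in the first 21.5 h. They do not show that a reported median would be wrong by any given amount. For a descriptive secondary endpoint this is a change that should be made, and it does not touch the primary safety objective.

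**What to change.** 1. Reconcile Protocol 8.1 criterion 2a, Protocol 10.1.1 and SAP 1.1 on the symptom severity needed for entry by a positive test.
2. In SAP 3.3.8 and 5.2.2, base the main time-to-alleviation estimate (Table 14.2.2.1, Figures 14.2.2.2 to 14.2.2.4 and 14.4.2) on ITTI subjects with at least one of the seven symptoms rated moderate or severe at the pre-dose assessment.
3. State which rating decides this: the pre-dose diary entry, or the staff Screening rating if that entry is missing. The fallback is needed because Protocol 10.1.2.2 lists diary training among the post-dose procedures, so some subjects may have no pre-dose entry.
4. Report the number excluded by age group, and show the whole-ITTI estimate as supportive.

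The cost is SAP wording and one supportive display; the symptoms are already rated at Screening. Some subjects may leave the main estimate: at an assumed 20%, up to 24 of 120 (0.20 × 120) if all 120 were in the ITTI population. If none is excluded, the result is unchanged and the report can say so.

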3.4. TIMING OF ANALYSES

If final results to analyze secondary virologic or PK endpoints are delayed unexpectedly and significantly, then analysis of the clinical data will proceed based on cleaned and locked clinical CRF data and virologic data to identify the intent-to-treat infected (ITTI) population, and analysis of the secondary virologic and PK endpoints will be performed based on available preliminary results. A final analysis of secondary virologic and PK endpoints will be conducted once final data are available.

Secondary analyses to evaluate the exposure response of peramivir, and to assess changes in influenza viral susceptibility to neuraminidase inhibitors following treatment, may be conducted at a later date if the required PK and virology data are not available at the time of the analysis of the clinical data.

4. ANALYSIS POPULATIONS

All subjects enrolled (eg, signed the informed consent) will be included in the summary of subject disposition and all data listings. The populations for analysis of safety and effectiveness endpoints will include the intent-to-treat (ITT), ITTI, safety, and exposure-response populations.

4.1. INTENT-TO-TREAT POPULATION

The ITT population will include all enrolled subjects. The ITT population will be the primary population for analyses of demography and subject accountability.

4.2. INTENT-TO-TREAT INFECTED POPULATION

The ITTI population will include all subjects who are enrolled, treated, and have influenza type A or B confirmed by PCR. The ITTI population will be used for analyses of effectiveness.

4.3. SAFETY POPULATION

The safety population will include all enrolled subjects who receive any amount of study drug. The safety population will be the primary population for all analyses of safety data.

4.4. EXPOSURE-RESPONSE POPULATION

The exposure-response population will include all subjects in the ITTI population who have a quantifiable peramivir concentration on Day 1 and have at least one post-baseline effectiveness assessment. This population will be used for all exposure-response analyses.

5. STATISTICAL METHODS

Descriptive statistical methods will be used to summarize the data from this study. Data will be summarized by age group and study day/time, if appropriate. Unless stated otherwise, the term “descriptive statistics” refers to number of subjects (n), mean, median, standard deviation (SD), minimum, and maximum for continuous data and frequencies and percentages for categorical data. The term "age group" refers to the following: < 65 years, 65-75 years, > 75 years, and ≥ 65 years. Note that 65-75 years and > 75 years are subsets of the ≥ 65 years group. No formal statistical hypothesis testing is planned.

All data collected during the study will be included in data listings. Unless otherwise noted, the data will be sorted first by age group, subject number, and then by date within each subject number.

The statistical analyses will be conducted with the SAS® software package version 9.4 or higher. All analyses will be subject to formal verification procedures. Specifically, results will be verified utilizing independent programming prior to issuance of the draft statistical report. All documents will be verified by the lead statistician to ensure accuracy and consistency of analyses.

